Appendix 2: ECOG Performance Status Scale

Appendix 3: Cockcroft-Gault estimation of CrCL

Appendix 4: International Prognostic Scoring System (IPSS) for MDS

Appendix 5: NCI CTC Version 4.0

Appendix 6: Correlative Studies

1 PROTOCOL SYNOPSIS

PROTOCOL TITLE:PHASE II STUDY OF LENALIDOMIDE AND ELTROMBOPAG IN PATIENTS WITH SYMPTOMATIC ANEMIA IN LOW OR INTERMEDIATE I MYELODYSPLASTIC SYNDROME (MDS)	
DATE PROTOCOL FINAL:	08 JULY 2011
INDICATION:	MDS
STUDY PHASE:	Phase II

BACKGROUND AND RATIONALE:The rationale for this study is that combined treatment with eltrombopag (PROMACTA) and lenalidomide (REVLIMID) will reduce the incidence of lenalidomide induced thrombocytopenia thus enabling patients to tolerate the required duration of lenalidomide therapy leading to higher rates of response to lenalidomide. A major reason why lenalidomide cannot be used for the treatment of MDS is because of the occurrence of thrombocytopenia. The use of eltrombopag will potentially raise platelet counts in these patients and enable a longer exposure to lenalidomide. Secondly, thrombocytopenia in the first 2 months after lenalidomide therapy predicts the subsequent response to lenalidomide treatment in patients with low risk MDS. Thus raising platelet counts to enable continuation of Lenalidomide therapy is important in these patients. Lastly, an increase in blasts has been a potential concern with the use of thrombopoietin mimetics. Preclinical studies have indicated that eltrombopag is less likely to increase blasts thus making it a possible potential therapeutic candidate in low risk MDS.
	

STUDY OBJECTIVES:
 
Primary Objectives:
 
To evaluate the rate of hematologic improvement of the eltrombopag/lenalidomide combination as defined by the IWG 2006 criteria
 
To evaluate the safety and tolerability of the eltrombopag/lenalidomide combination in patients with low –intermediate risk MDS
 
Secondary Objectives
 
To compare the time to hematologic improvement
 
To evaluate the duration of hematologic improvement
 
To evaluate the effect of combination treatment on platelet counts, platelet transfusions and bleeding events.
 
To evaluate the frequency of bone marrow response (CR+PR) and cytogenetic response.
 
To evaluate the relationship between mutations in bone marrow stem cells and response
 
To evaluate the relationship between various stem and progenitor alterations and response
	

STUDY DESIGN:
 
This is a multicenter, phase II study evaluating the efficacy and safety of the combination of lenalidomide and eltrombopag in low risk MDS.
	

Patients will be treated based on their baseline platelet counts:

Arm A: Patients with platelet counts $\geq 50k$ at baseline:

These patients will start Len at 10mg/d for 3 weeks/month, and will not start eltrombopag until the platelet counts drop below 50,000. If platelets drop less than 50,000, Len will be stopped and eltrombopag will be started at a dose of 100mg initially (50 mg for subjects of East Asian heritage) and titrated up to a maximum dose of 300 mg (150 mg for subjects of East Asian heritage) to achieve a platelet count above 50,000/L. Once a platelet count above 50,000 is achieved, the same dose of eltrombopag will be continued for an additional two weeks. Once a platelet count $> 50,000$ is maintained for two weeks, eltrombopag will be discontinued and Len will be started as a single agent. If the platelets again fall below 50,000 then Len will be stopped and eltrombopag will be re-initiated at the dose that was last given to the patient. Once the platelets are increased to above 50,000 and maintained at this level for 2 weeks, Len will be started again and this time will be given concurrently with eltrombopag. These agents will subsequently be used concurrently for all subsequent cycles.

Arm B: Patients with Plts $< 50k$ at baseline

These patients will not receive Len initially. Eltrombopag will be started alone at a dose of 100mg initially and titrated up (Table 4) to achieve a platelet count above 50,000. Once the platelet count above 50,000 is achieved, the same dose of eltrombopag will be continued for an additional two weeks. Once the plt count $> 50,000$ is maintained for two weeks, the patients will discontinue eltrombopag and follow the treatment algorithm described for patients in arm A.

[figure not shown]

Figure 1: Schema of the study (* starting dose of Eltrombopag for Asian subjects is 50mg)

STUDY ENDPOINTS

Primary:

Hematologic improvement

Secondary: Time to attain and duration of hematologic improvement Bone marrow morphologic and cytogenetic response Platelet counts and Bleeding events
	

STUDY DURATION:2 years
	
TOTAL SAMPLE SIZE:52patients


DOSING REGIMEN(S): The lenalidomide starting dose will be based on baseline calculated creatinine clearance (see Appendix 3). Eltrombopag starting dose will be 100mg (50mg for patients with east Asian descent) and dosing will be based on regimen as detailed in protocol.
	
DRUG SUPPLIES: For study participants, Celgene Corporation will provide lenalidomide at no charge through the Revlimid REMS™program. GSK will provide eltrombopag at no charge.

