5 INVESTIGATIONAL PLAN

5.1 Overall design

This is a multicenter, Phase II study evaluating the efficacy and safety of the combination of lenalidomide and eltrombopag in low risk MDS. This study will include patients with low risk MDS (IPSS low and Int-1) with symptomatic anemia or transfusion dependence. Patients will be treated in 2 separate arms based on their baseline platelet counts:

Arm A : Patients with platelet counts $\geq 50k$ at baseline:

These patients will start Len at 10mg/d for 3 weeks/month, and will not start Eltrombopag until the platelet counts drop below 50,000. If platelets drop less than 50,000, Len will be stopped and Eltrombopag will be started at a dose of 100mg initially and titrated up (similar schema to 509 study) to achieve a platelet count above 50,000. Once the platelet count above 50,000 is achieved, the same dose of Eltrombopag will be continued for an additional two weeks. Once a platelet count $> 50,000$ is maintained for two weeks, Eltrombopag will be discontinued and Len will be started as a single agent. If the plts again fall below 50k then Len will be stopped and Eltrombopag will be re-initiated at the dose that was last given to the patient. Once the platelets are increased to above 50,000 and maintained at this level for 2 weeks, Len will be started again and this time will be given concurrently with Eltrombopag. These agents will now be used concurrently for all subsequent cycles.

Arm B: Patients with Plts $< 50k$ at baseline

These patients will not receive Len initially. Eltrombopag will be started alone at a dose of 100mg initially and titrated up (similar schema to 509 study) to achieve a

platelet count above 50,000. Once the platelet count above 50,000 is achieved, the same dose of eltrombopag will be continued to additional two weeks. Once the plt count > 50,000 is maintained for two weeks, the patients will discontinue eltrombopag and follow the treatment algorithm described for patients in arm A. Patients that never drop their platelet counts below 50,000 will not receive any additional eltrombopag. (Figure 1)

Treatment with myeloid growth factors is permitted for the management of neutropenia at the discretion of the treating investigator.

Study drugs will be continued until disease progression or unacceptable toxicities.

Bone marrow examinations will be performed at baseline, at every 4 months and at study discontinuation.

52 evaluable adult subjects with MDS will be evaluated.

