8.1.2 Dose Modifications

Dose Reductions for lenalidomide

Table 1 gives the dose levels for the dose reduction steps for adverse events.

Table 1: Dose Reduction Steps for lenalidomide

Starting dose 10 mg/day on days 1-21, followed by 7 days of no therapy

Dose level -1 5 mg daily

Dose level -2 5 mg every other day (qod)

Patients who experience limiting neutropenia after prolonged treatment with 5 mg every other day may resume treatment at the same dose upon hematologic recovery.

Dose Modifications for Neutropenia

Hold lenalidomide for a decline in neutrophil count to $< 500/\mu\text{L}$ that does not respond to myeloid growth factor administration. Lenalidomide should be resumed at the next dose

reduction step when neutrophil count is $> 500/\mu\text{L}$. **Dose Modifications for Thrombocytopenia**

For patients with a baseline platelet count $< 50,000/\mu\text{L}$;

Start eltrombopag when the platelet count is $< 50,000/\mu\text{L}$. Start Lenalidomide (AND STOP eltrombopag) only after platelet count $> 50,000$ (non transfused) for at least 2 weeks. If platelet fall $< 50,000/\mu\text{L}$ after resuming lenalidomide again then again hold dose and start Eltrombopag again. Once plt count $> 50,000$ for two weeks, then start lenalidomide and give eltrombopag concomitantly.

For patients with a baseline platelet count $\geq 50,000/\mu\text{L}$;

Start Lenalidomide alone. If plt count falls below $50,000/\text{L}$ then follow algorithm as above.

Patients who do not experience platelet recovery within 8 weeks of starting Eltrombopag should be removed from study and complete all off study evaluations.

Dose modifications for hemoglobin levels:

For those patients experiencing a rise in hemoglobin $> 14 \text{ g/dL}$, Lenalidomide should be withheld until the hemoglobin is $< 12 \text{ g/dL}$, at which time treatment can be resumed according to the dose adjustment recommendations in Table 1. For those patients previously adjusted to the lowest CC-5013 (lenalidomide) dose, the CC-5013 (lenalidomide) schedule should be changed to a 2 week treatment schedule every 4 weeks.

Dose Modifications for Other Adverse Events

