Appendix 3: Cockcroft-Gault estimation of CrCl:

Cockcroft-Gault estimation of creatinine clearance (CrCl):
(Cockcroft, 1976; Luke 1990)

$$\text{CrCl (mL/min)} = \frac{(140 - \text{age}) \times (\text{weight, kg})}{72 \times (\text{serum creatinine, mg/dL})}$$

(Males)

$$\text{CrCl (mL/min)} = \frac{(140 - \text{age}) \times (\text{weight, kg})}{72 \times (\text{serum creatinine, mg/dL})} \times 0.85$$

(Females)

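### The synopsis makes the lenalidomide starting dose depend on creatinine clearance, but no text converts a clearance into a dose, and the dosing text starts everyone at 10 mg/day

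*Combined protocol and SAP*

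**What the plan says.** The Dosing Regimen(s) box of the synopsis (section 1) states: "The lenalidomide starting dose will be based on baseline calculated creatinine clearance (see Appendix 3". The table of contents lists that appendix as "Appendix 3: Cockcroft-Gault estimation of CrCL". The appendix opens with "Cockcroft-Gault estimation of creatinine clearance (CrCl" and gives one formula for men and the same formula times 0.85 for women.

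The dosing text has no renal condition:

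- Synopsis, study design, Arm A: "These patients will start Len at 10mg/d for 3 weeks/month".
- Section 5.1, Arm A: "10mg/d for 3 weeks/month, and will not start Eltrombopag until" platelets fall below 50,000.
- Section 5.1, Arm B: after platelet recovery on eltrombopag, patients "follow the treatment algorithm described for patients in arm A".
- Section 8.1.2, Table 1 (lenalidomide reduction steps): "Starting dose 10 mg/day on days 1-21, followed by 7 days of no therapy".

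Section 8.1.1, although headed Dosing regimen, states no dose. Section 5.2.1 says that the kidney excretes most lenalidomide unchanged, about two-thirds of it in healthy volunteers.

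**The concern.** One sentence makes the first dose a function of clearance. Every place that gives a number makes it a constant. The two cannot both be followed for a patient whose renal function calls for something other than 10 mg.

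A physician who follows sections 5.1 and 8.1.2 starts a renally impaired patient at full dose. A physician who follows the synopsis knows that clearance should govern the dose and has the formula, but must choose the dose without a rule. Section 5.1 says: "This is a multicenter, Phase II study evaluating the efficacy and safety". Across several centres, similar patients could start at different doses, and each choice would depart from one of the protocol's own statements.

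Safety and tolerability is a primary objective. Section 3.4 reports that neutropenia (67%) and thrombocytopenia (57%) were dose limiting in the earlier 43-patient lenalidomide monotherapy study, so the first dose deserves a clear rule.

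**Working it through.** There is no stated figure to reproduce. The check sets side by side every part of the protocol that fixes or changes the lenalidomide dose or mentions renal function.

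1. **Does Appendix 3 supply a dose?** No. Its inputs are age, weight, serum creatinine and sex, and its output is a clearance in mL/min. It has no clearance bands and no doses, and its title promises none.

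2. **Does another section supply one?** No.
   - Section 8.1.1 covers toxicity grading, delays to response assessment and adverse-event review.
   - Table 1 in section 8.1.2 lists 5 mg daily and 5 mg every other day, but as reduction steps for adverse events, not as starting doses.
   - The other triggers in section 8.1.2 are neutrophils, platelets, hemoglobin and specified toxicities. None is renal.
   - The renal-impairment text in section 5.2.2 concerns eltrombopag only.

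3. **Does eligibility keep renally impaired patients out?** No. Section 6.1 has 17 inclusion criteria and section 6.2 has 7 exclusion criteria: 17 + 7 = 24, of which 0 set a creatinine or clearance limit.

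4. **How many statements fall on each side?** One sentence ties the starting dose to clearance (synopsis dosing box). Three places state 10 mg/day without a renal condition: the synopsis design text, section 5.1 and Table 1. The synopsis therefore conflicts with itself as well as with the body. Platelets decide when lenalidomide starts, but not the starting dose.

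5. **Could the rule have been lost from the text as read?** This is unlikely. Five figures are missing and there are five captions: study schema, two chemical structures, eltrombopag dose adjustment and blast monitoring. None concerns renal dosing. Placing the missing figure in section 8.1.2 as Figure 4 is an inference, because its caption stands some paragraphs later. More decisively, the synopsis sends the reader to Appendix 3, and Appendix 3 is present.

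6. **Does the protocol show how such a condition should be carried through?** Yes. The same synopsis box gives eltrombopag at 100 mg, or 50 mg for East Asian patients, and section 8.1.2 repeats that condition with full numbers. The lenalidomide condition has no counterpart there.

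7. **Can the formula be computed from scheduled data?** Not demonstrably. Creatinine is in the screening chemistry (section 2, note 5). Weight is not listed in the schedule. A physical examination is scheduled, but the protocol does not say that it includes weight. Section 10.3.2 asks for weight in adverse-event reports, which is not a pre-dose requirement.

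**The case against.** The strongest reply is that this is an omission and not a contradiction: 10 mg is the nominal dose, a renal adjustment was intended, and its table was never written. Table 1 exists mainly to list reduction steps. That reading of intent is plausible, but it leads to the same place. The adjustment cannot be carried out, and the text as written gives 10 mg to everyone.

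A second reply is that safeguards limit the consequence. Chemistry and blood counts are weekly for the first 4 weeks. Lenalidomide stops when platelets fall below 50,000, and it is held for neutrophils below 500 that do not respond to growth factor. Lower dose levels are available. This stands as mitigation, but all of it acts after the first dose has been given.

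A third is that a table may have been lost. Table numbering is irregular: the eltrombopag adjustment table is cited as Table 4 in the synopsis and Table 3 in section 8.1.2, but captioned Table 2. Loose numbering is a sufficient explanation, and the synopsis points to an appendix and not to a table.

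Three stronger readings are tempting, and the documents do not support them. A reader might infer that renally impaired patients will be harmed to some known degree, but the protocol gives no lenalidomide exposure or toxicity data by renal function and no baseline renal distribution. A reader might infer that the two-stage design is compromised, but nothing in section 14.2 depends on the starting-dose rule. A reader might infer that a minimum clearance for entry is required, but the documents offer no threshold, and that is a separate eligibility decision.

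**Conclusion.** The point holds. The synopsis rule for the lenalidomide starting dose cannot be carried out, and the text that can be carried out runs against it: three unconditional statements of 10 mg/day, no clearance-to-dose rule, and no renal limit among 24 criteria. As written, a renally impaired patient can enroll and receive the full first dose of a mainly renally excreted drug.

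The conclusion assumes that the readable text is complete on this point, which the pointer to a present Appendix 3 supports. It makes no claim about how many patients are affected, how far exposure would change, or any effect on response or toxicity. It is a safety-relevant instruction that needs to be settled, not a flaw in the sample size or error rates.

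**What to change.** Add to section 8.1.2 one table of clearance bands and lenalidomide starting doses. The sponsor should supply the values from the labelling or the Investigator's Brochure, because the documents contain none. Make the 10 mg/day in the synopsis design text, section 5.1 and Table 1 conditional on that table; Arm B follows by reference. Point the synopsis sentence to the table and keep Appendix 3 for the formula. List body weight at screening in section 2 so that the formula can be computed.

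If a flat 10 mg is intended for all, delete the synopsis sentence. A minimum clearance for entry would then be an optional, separate choice for the sponsor.

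The cost is a short amendment, one added screening item and a lower starting dose for some patients. Under section 15.2 the amendment needs review by both drug suppliers and approval by the Einstein IRB. If it is judged to affect subject safety significantly, as a starting-dose change plausibly would be, it also needs approval by the IRB at each participating centre.

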2 SCHEDULE OF STUDY ASSESSMENTS

	Screening Assessment (30 days prior to initiation)	Weekly	Every 28 days (Day 1 of each cycle)	Week 16 and treatment discontinuation	Follow up ¹¹
Medical History	x				
Prior MDSTreatment	x				
ECOG Performance Status	x	X ⁸	x		
Pregnancy test ¹	x ²		x ³	X	
Serum ferritin level	x			X	
Serum erythropoietin	x				
Thyroid function tests ⁴	x			X	
aaPT/PTT/INR	x				
Serum chemistry ⁵	x	X ⁸	x	X	
Hematology, peripheral blood smear and RBC transfusion history ⁶	x ⁷	x ⁸	x	X	x
Physical examination	x		x	x	x
ECG	x		x ¹²		
Review medication log			x		
Response				x	

assessment ⁹					
Bone marrow aspirate & biopsy ¹⁰	X			X	
Cheek swab and toe nail clipping	X				

1. Women of childbearing potential only. Serum or urine pregnancy testing for β-HCG with a sensitivity of at least 50 mIU/mL. For further requirements for pregnancy testing and birth control, please see Appendix 1.
					

2. Within 7 days prior to the first day of study therapy.
					

3. Every 4 weeks while on study drug.
					

4. TSH (thyroid-stimulating hormone), T3, and T4 levels. Repeat thyroid function tests every three months.
					

5. Includes sodium, potassium, chloride, CO₂, calcium, magnesium, phosphorus, blood urea nitrogen (BUN), creatinine, glucose, albumin, total protein, alkaline phosphatase, total bilirubin, aspartate transaminase (SGOT/AST) or glutamic pyruvic transaminase (SGPT/ALT), lactate dehydrogenase (LDH), and uric acid.
					

6. Red blood cell (RBC) count, reticulocyte count, hemoglobin, hematocrit, white blood cell (WBC) count and differential, absolute neutrophil count (ANC), and platelet count required for protocol therapy must be done < 24 hours prior to the treatment cycle. Pretreatment CBC with differential and LFT's should be done < 1 week before randomization.
					

7. If not obtained within 7 days of the first day of study therapy, repeat the CBC on Day 0 of study treatment prior to start of study therapy.
					

8. Perform weekly for 4 weeks, then every 2 weeks for 5 to 8 weeks and monthly thereafter. Weekly CBC should be done when titrating or starting eltrombopag dosing until a stable platelet count is achieved.
					

9. Hematologic, pathologic, and cytogenetic response will be assessed according to criteria outlined in Section 6.1.2.
					

10. Bone marrow aspirate and biopsy with cytogenetic analysis and iron stains will be performed pre-study, and after 16 weeks of study treatment, and at the time of final response analysis. Additional biological studies obtained with bone marrow aspiration
					

are summarized in Section 14.

11. Every 3 months if patient is < 2 years from study entry, every 6 months if patient is 2-5 years from study entry, every 12 months if patient is 5-10 years from study entry. No specific requirements if patient is more than 10 years from study entry.

12. Only for patients receiving 300 mg eltrombopag dose or higher, resting 12-lead ECG will be obtained pre-dose on Day 1. A post-dose ECG should be obtained at Tmax (3 hours); if assessment cannot be performed at 3 hours, record actual time ECG was performed within a 2-6 hour window post-dose. A pre- and post-dose ECG as described above is required Week 2, week 4, 8 and 16.

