6.3 Visit schedule and assessments

Screening Assessments and all on study scheduled visits and assessments are outlined in Section 2 Table of Study Assessments.

At treatment discontinuation, subjects will undergo off study evaluations per the Schedule of Assessments, Section 2. In addition, a safety assessment will be done approximately 28 days post the last dose of protocol therapy.

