8.3 DURATION OF THERAPY

Patients will receive protocol therapy unless:

1. Extraordinary Medical Circumstances: If at any time the constraints of this protocol are detrimental to the patient's health, protocol treatment should be discontinued
2. Patient withdraws consent.

3. Adverse event(s) (AEs) occur that, in the judgment of the Investigator, may cause severe or permanent harm or which rule out continuation of study drug.
4. Lack of therapeutic effect
5. Patient's disease converts to acute myeloid leukemia or disease progression.
6. Patient is lost to follow-up.
7. if a patient has a QTc >500 msec or QT >600 msec;
8. if a patient meets any of the following liver chemistry threshold criteria:
 ALT \geq 3xULN and bilirubin \geq 1.5xULN (>35% direct). ALT \geq 5xULN.

ALT \geq 3xULN if associated with the appearance or worsening of hepatitis symptoms or rash.

All subjects who discontinue study medication should continue to participate in the follow-up visits.

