Serum ALT, AST, and bilirubin should be measured prior to initiation of eltrombopag, every 2 weeks during the dose adjustment phase and monthly following establishment of a stable dose. If bilirubin is elevated, perform fractionation. Evaluate abnormal serum liver tests with repeat testing within 3 to 5 days. If the abnormalities are confirmed, monitor serum liver tests weekly until the abnormality(ies) resolve, stabilize, or return to baseline levels. Permanently discontinue eltrombopag if ALT levels increase to $\geq 3X$ the upper limit of normal (ULN) and are:

- progressive, or
- persistent for ≥ 4 weeks, or
- accompanied by increased direct bilirubin, or
- accompanied by clinical symptoms of liver injury or evidence for hepatic decompensation.

Pharmacokinetic evaluations in patients with hepatic impairment show that plasma eltrombopag $AUC_{(0-\tau)}$ increases with increasing degree of hepatic impairment (as measured by Child-Pugh). Exercise caution when administering eltrombopag to patients with hepatic impairment (Child-Pugh Class A, B, C). Use a lower starting dose of eltrombopag in patients with any degree of hepatic impairment i.e. cirrhosis and monitor closely

Bone Marrow Reticulin Formation and Risk for Bone Marrow Fibrosis

Eltrombopag is a thrombopoietin (TPO) receptor agonist and TPO-receptor agonists may increase the risk for the development or progression of reticulin fiber deposition within the bone marrow.

In the ITP extension study, 151 patients have had bone marrow biopsies evaluated for increased reticulin and collagen fiber deposition. Bone marrow biopsies taken after 1 year of therapy showed predominantly myelofibrosis (MF) Grade 1 or less in 140/151 (93%) of patients. There were 11/151 (7%) of patients with MF Grade 2. Four patients had collagen deposition reported. One patient with a pre-existing MF Grade 1 developed a MF Grade 2 and subsequently discontinued treatment with eltrombopag. Clinical studies have not yet excluded a risk of bone marrow fibrosis with cytopenias.

Prior to initiation of eltrombopag, the peripheral blood smear should be examined closely to establish a baseline level of cellular morphologic abnormalities. Following identification of a stable dose of eltrombopag, peripheral blood smears and CBCs should be examined monthly for new or worsening morphological abnormalities (e.g., teardrop and nucleated red blood cells, immature white blood cells) or cytopenia. If the patient

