develops new or worsening morphological abnormalities or cytopenia, treatment with eltrombopag should be discontinued and a bone marrow biopsy, including staining for fibrosis considered.

Recurrence of Thrombocytopenia After Cessation of Eltrombopag

Discontinuation of eltrombopag may result in recurrence of thrombocytopenia. This recurrence of thrombocytopenia may increase the patient's risk of bleeding, particularly if eltrombopag is discontinued while the patient is on anticoagulants or antiplatelet agents. In the 3 controlled ITP clinical studies, transient decreases in platelet counts to levels lower than baseline were observed following discontinuation of treatment in 8% and 8% of the eltrombopag and placebo groups, respectively. Serious hemorrhagic events requiring the use of supportive ITP medications occurred in 4 severely thrombocytopenic patients within one month following the discontinuation of eltrombopag; none were reported among patients in the placebo group.

Following discontinuation of eltrombopag, weekly CBCs, including platelet counts for at least 4 weeks should be obtained and alternative treatments for recurrence of thrombocytopenia, according to current treatment guidelines, considered.

Thrombotic/thromboembolic complications

Eltrombopag may increase the risk of thrombotic/thromboembolic events.. Excessive doses of eltrombopag may increase platelet counts to a level that produces thrombotic/thromboembolic complications.

In the 3 controlled ITP clinical studies, thrombotic/thromboembolic complications occurred in four patients in the groups that received eltrombopag and none in the placebo groups. Thrombotic/thromboembolic complications have also been reported in the ITP extension study. The thrombotic/thromboembolic complications in patients with chronic ITP included both venous and arterial events and were observed at low and normal platelet counts.

Use caution when administering eltrombopag to patients with known risk factors for thromboembolism (e.g., Factor V Leiden, ATIII deficiency, antiphospholipid syndrome, chronic liver disease). To minimize the risk for thrombotic/thromboembolic complications, do not use eltrombopag in an attempt to normalize platelet counts. Follow the dose adjustment guidelines to achieve and maintain a platelet count of $\geq 50 \times 10^9/L$ as necessary to decrease the risk for bleeding

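### Footnote 5 accepts AST or ALT, so on lenalidomide alone the schedule does not assure the ALT value that the Section 8.3 liver stopping rule needs

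*Combined protocol and SAP*

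**What the plan says.** **Scheduled panel.** Section 2, footnote 5, defines serum chemistry. It includes total bilirubin, alkaline phosphatase and "aspartate transaminase (SGOT/AST) or glutamic pyruvic transaminase (SGPT/ALT", that is, one transaminase of the site's choosing.

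**Scheduled frequency.** Footnote 8 says: "Perform weekly for 4 weeks, then every 2 weeks for 5 to 8 weeks and monthly thereafter". The only test it adds for eltrombopag is a blood count: "Weekly CBC should be done when titrating or starting eltrombopag dosing until a stable platelet count is achieved". Section 6.3 treats the table as the full list, saying that "all on study scheduled visits and assessments are outlined in Section 2 Table of Study Assessments".

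**Stopping rule.** Section 8.3 opens with "Patients will receive protocol therapy unless", and item 8 applies "if a patient meets any of the following liver chemistry threshold criteria". The three criteria are:
- ALT at least 3 times the upper limit of normal (ULN) with raised, mainly or partly direct bilirubin;
- ALT at least 5 times ULN;
- ALT at least 3 times ULN with hepatitis symptoms or rash.

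AST is not named, and the rule is not restricted to time on eltrombopag.

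**Eltrombopag monitoring.** Section 9.2 asks for ALT, AST and bilirubin before eltrombopag is begun, then "every 2 weeks during the dose adjustment phase and monthly following establishment of a stable dose". Once eltrombopag is stopped, the instruction is: "Following discontinuation of eltrombopag, weekly CBCs, including platelet counts for at least 4 weeks should be obtained". Liver tests continue after that point only if an abnormality was already being followed.

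**The concern.** A rule that ends treatment should rest on a measurement that the schedule guarantees. Here the schedule guarantees a transaminase, while the rule needs one particular transaminase. Section 9.2 supplies it around eltrombopag but not in the periods on lenalidomide alone. Section 9.1 lists ALT among the laboratory events possibly related to lenalidomide, so the rule is relevant in those periods too. In a multicenter trial, whether the rule can be applied would then depend on local laboratory habit.

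A smaller mismatch concerns timing. Eltrombopag can start late, because Arm A patients receive it only after a platelet fall. By then scheduled chemistry may be monthly, whereas Section 9.2 wants 2-weekly liver tests while the dose is being adjusted. A site working from the table alone could take a dose step before any scheduled liver test on the drug.

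**Working it through.** The plan states no figure on this point to reproduce. The check compares the texts and then counts visits.

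**1. Which requirement supplies ALT, and when**

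| Treatment period | Source of period | Is ALT required? |
|---|---|---|
| Arm A from the start until platelets fall below 50,000 | 5.1 | Not by footnote 5; 9.2 does not apply beyond its test before eltrombopag |
| Eltrombopag alone, either arm | 5.1, 8.1.2 | Yes, by 9.2 |
| Lenalidomide alone after the first eltrombopag course, either arm | 5.1, 8.1.2 | Not by footnote 5; 9.2 asks for blood counts |
| Both drugs together, after a second fall | 5.1, 8.1.2 | Yes, by 9.2 |

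Arm A begins on lenalidomide alone, and Arm B stops eltrombopag when lenalidomide starts. So everyone who receives lenalidomide has at least one period in which ALT is not specifically required. For the patients in Section 14.2 who may never need eltrombopag (assumed 10-20% of those with platelets above 50,000), that period is the whole treatment.

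**2. Scheduled draws on lenalidomide alone up to week 16**

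Footnote 8 can be read in two ways, counting the pretreatment draw as week 0:
- 2-weekly within weeks 5 to 8: weeks 0, 1, 2, 3, 4, 6, 8, 12, 16 = 9 draws.
- 2-weekly for 8 further weeks: weeks 0, 1, 2, 3, 4, 6, 8, 10, 12, 16 = 10 draws.

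Under either reading, none of these must include ALT. Footnote 6 asks for pretreatment liver function tests without naming ALT.

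**3. Frequency, for eltrombopag started in the monthly phase**

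Inputs: monthly draws are 28 days apart, and dose steps are possible every 2 weeks (8.1.2). The window is 8 weeks, taken from the 8.1.2 limit for removal without platelet recovery. That window is an assumption.

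Section 9.2 then asks for:
- 4 panels (days 0, 14, 28, 56) if the dose is stable from day 28;
- 5 panels (days 0, 14, 28, 42, 56) if adjustment continues throughout.

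For a start *k* days after a monthly draw, the scheduled draws fall on days −*k*, 28−*k* and 56−*k*. Section 9.2 sets no window for the test before eltrombopag, so the preceding monthly draw counts as baseline:

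| *k* | Draw days | Panels | Short of 4 | Short of 5 |
|---|---|---|---|---|
| 1 | −1, 27, 55 | 3 | 1 | 2 |
| 7 | −7, 21, 49 | 3 | 1 | 2 |
| 14 | −14, 14, 42 | 3 | 1 | 2 |
| 21 | −21, 7, 35 | 3 | 1 | 2 |

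The shortfall is 1 to 2 panels in every case. The first on-drug draw falls after day 14 when 28−*k* > 14, that is for *k* = 0 to 13, which is 14 of the 28 possible start days. For *k* = 1 it falls on day 27, after a possible day-14 step from 100 to 200 mg.

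**4. Earlier starts**

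A week-0 start has draws at weeks 0, 2, 4, 6 and 8 under both readings, so there is no shortfall. A week-4 start has draws at weeks 4, 6, 8 and 12 under the first reading, which meets the 4-panel case and is one short of 5. Under the second reading it has all 5.

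**The case against.** **A site can satisfy both texts by running ALT.** Footnote 5 permits ALT, and Section 8.3 is itself binding, so a careful site would choose ALT. This stands. A reader might infer that the stopping rule cannot be applied at all on lenalidomide alone. The documents do not support that: the rule fails only where a site runs AST without ALT, and nothing shows that any site does.

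**Patients on lenalidomide alone are still monitored.** One transaminase, total bilirubin and alkaline phosphatase are measured. Section 8.1.2 holds lenalidomide for related non-hematologic toxicity of Grade 3 or higher. Section 10.3 requires the investigator to appraise every abnormal laboratory result, so a raised AST would probably prompt an ALT. This largely stands. What remains is an ALT threshold crossed without a notable change in AST or bilirubin, and the documents give no frequency for that. The 8.1.2 hold is not a substitute: it depends on attribution to lenalidomide and allows treatment to resume at a lower dose, whereas 8.3 ends therapy.

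**Item 8 may have been meant for eltrombopag only.** The text does not say so. If that was the intent, 8.3 is the place to state it.

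**The frequency point repeats an instruction already in force.** This stands. Section 9.2 requires the 2-weekly tests, and a site that follows it has no gap. The point concerns agreement between two sections, not missing monitoring.

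**Two further inferences go too far.** A shortfall of 3 panels arises only if the baseline draw must fall on the day of the start or the day before. Starts 7, 14 or 21 days after a monthly draw would then count 2 panels, and 5 − 2 = 3, but Section 9.2 sets no such window. Nor does Section 9.2 state a requirement for tests before a restart. A restart uses the last dose given (5.1), so it adds no dose step by itself.

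**Conclusion.** The point holds in limited form. The schedule's choice of transaminase does not match the stopping rule, and Section 9.2 does not close the gap on lenalidomide alone. A site that runs only AST there is within the schedule but cannot be assured of applying 8.3 item 8.

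The exposure is some part of treatment for everyone who receives lenalidomide, and all of it for the assumed 10-20% group. The number of patients actually affected depends on how many sites run AST alone, which is unknown and may be zero. No endpoint, sample size or analysis is touched; this is a safety-monitoring correction that should be made because it is nearly free.

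The frequency mismatch is secondary: 1 to 2 panels over an assumed 8-week window, for eltrombopag starts in the monthly chemistry phase only. The documents do not say how many patients will start then.

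**What to change.** **Footnote 5:** change *or* to *and* between AST and ALT. The cost is one added analyte at sites that run only AST, and nothing elsewhere.

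**Footnote 8:** add a cross-reference such as: ALT, AST and bilirubin before eltrombopag initiation and every 2 weeks during dose adjustment, per Section 9.2. This puts about 1 to 2 further liver panels into the table for each start in the monthly phase. They can use the visits already made for the weekly blood count. Sites already following Section 9.2 have no added panels.

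A liver panel before each eltrombopag restart would be a sensible addition. If adopted, it should be written as a new requirement and not attributed to Section 9.2.
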